#### 9.1.1.6 β-Score: a composite index of post-transplant graft function

The  $\beta$ -score will be determined from the HbA1c, insulin requirements, fasting (basal) glucose, and stimulated c-peptide as developed by Ryan et al. The score may range from 0 (no graft function) to 8, with all subjects reported with a score of 8 also having 90-minute glucose levels during a MMTT that are  $\leq 10.0 \text{ mmol/L}$  (180 mg/dL), indicative of excellent graft function.

#### 9.1.1.7 THE C-PEPTIDE TO GLUCOSE, CREATININE RATIO

The C-peptide to glucose, creatinine ratio (CPGCR) will be determined from the fasting (basal) glucose and c-peptide, and a simultaneous serum creatinine. This measure accounts for both the dependence of c-peptide secretion on the ambient glucose concentration and the dependence of c-peptide clearance on kidney function. The CPGCR is calculated as [c-peptide (ng/mL) \* 100]/ [glucose (mg/dL) \* creatinine (mg/dL)]. An index of islet graft function, this measure correlates well with both the 90-minute glucose levels during a MMTT and with the  $\beta$ -score.

All samples will be drawn according to the University of Washington (Seattle, WA) standard operating procedures and shipped frozen for measurement in the core laboratory. The acute insulin response to glucose (AIRglu) is calculated as the incremental area-under-the-curve for insulin between 0 and 10 minutes post-injection (the same calculation can be performed for C-peptide). Glucose effectiveness (SG), a measure of insulin-independent glucose disposal, and insulin sensitivity (SI), a measure of insulin-dependent glucose disposal, are derived from Bergman's minimal model using MinMod Millenium® software, and further allow for determination of the disposition index (DI = AIRglu · SI).

#### 9.1.1.9 CONTINUOUS GLUCOSE MONITORING SYSTEM® (CGMS)

Glucose variability and hypoglycemia duration will be determined using CGMS (Medtronic Minimed, Northridge, CA). CGMS involves the subcutaneous (SC) placement of a glucose sensor connected by tubing to a pager-sized monitoring device that stores glucose data over a 72-hour period. Subjects will have the sensor placed in the clinic and wear it continuously for 72 – 84 hours. Then they will drop the monitoring device off or ship it to the clinic 4 days later for analysis. Subjects will need to calibrate the sensor to their capillary BG readings 4 times daily with no interval between readings exceeding 12-hours. Data from each 72-hour period will be analyzed for mean glucose concentration, mean glucose variability (absolute value of measured glucose minus 5.5 mmol/L [100 mg/dl]), number and duration of hyper- (> 10.0 mmol/L [180 mg/dL]) and hypo- (< 3.0 mmol/L [54 mg/dL]) glycemic episodes, and total duration of hypoglycemia.

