### 4.1.3 Efficacy Endpoints

### At 75 ± 5 days following the first infusion:

- The percent reduction in insulin requirements
- HbA1c
- Mean amplitude of glycemic excursions (MAGE)
- Glycemic lability index (LI)
- Clarke hypoglycemia awareness score
- Ryan hypoglycemia severity (HYPO) score
- Basal (fasting) glucose and c-peptide and 90-min glucose derived from the mixed-meal tolerance test
- β-score
- C-peptide:glucose creatinine ratio
- Acute insulin response to glucose (AIRglu), insulin sensitivity, and disposition index derived from the insulin-modified frequently-sampled intravenous glucose tolerance (FSIGT) test
- Glucose variability and hypoglycemia duration derived from the continuous glucose monitoring system® (CGMS)
- The proportion of subjects with full islet graft function.

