### 9.1.1 Study Endpoints

Designated primary and secondary endpoints will be employed to compare each treatment group ("LMW-DS" and "State of the Art"). Because the assessment of islet graft function is dependent on complex physiologic relationships between the graft and its recipient, a number of different tests will be performed. The stimulated c-peptide for the Mixed Meal Tolerance Test (MMTT) will be used as the primary endpoint, and additional stimulatory tests of islet graft function utilizing glucose (FSIGT) challenges will be performed to assess secondary endpoints. Also, the effect of islet graft function on glycemic control (HbA1c), glycemic lability (MAGE and LI), hypoglycemia (Clarke and HYPO scores), glucose variability (CGMS), and quality of life (QOL) will be assessed as additional secondary endpoints. (See section 4.1 for endpoint description).

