#### 9.1.1.1 INSULIN REQUIREMENTS

Subjects will record their total daily insulin dose on self-monitoring diaries. Subject should be given exogenous insulin as needed to maintain fasting capillary glucose levels 5-9 mmol/L and avoiding hypoglycemia.

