#### 9.1.1.3 GLYCEMIC LABILITY

Glycemic lability will be assessed by both the mean amplitude of glycemic excursions (MAGE) and the lability index (LI).

The MAGE requires 14 – 16 capillary blood glucose (BG) measurements over two consecutive days taken before and 2-hours after breakfast, lunch, and dinner, and at bedtime with an optional measurement at 3 AM. A glycemic excursion is calculated as the absolute difference in peak and subsequent nadir (or vice versa) glucose values, with the direction (peak to nadir versus nadir to peak) determined by the first quantifiable excursion in the two day period. All excursions > 1 S.D. of the 7 – 8 glucose readings for the day in which they occurred qualify for the analysis, where they are summed and divided by the number of qualified excursions to give the MAGE in mmol/L (or mg/dL) glucose. A MAGE > 11.1 mmol/L (200 mg/dl) is indicative of marked glycemic lability.

The LI requires 4 or more daily capillary BG measurements over a 4 week period and is calculated as the sum of all the squared differences in consecutive glucose readings divided by the hours apart the readings were determined (range 1 to 12 hours) in  $(mmol/L^2/hr \cdot wk^{-1})$ . A LI greater than or equal to the 90th percentile (433 mmol/L/hr ·wk) of values derived from an unselected group of type 1 diabetes (T1D) patients is evidence for severe glycemic lability.

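### The CGMS glucose variability endpoint is defined as distance from a fixed 5.5 mmol/L, so it mixes glucose level with spread and a group difference cannot be read as a difference in variability

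*Protocol*

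**What the plan says.** Section 4.1.3 lists "Glucose variability and hypoglycemia duration derived from the continuous glucose monitoring system" among the efficacy endpoints at day 75 after the first infusion. The same item appears at day 365 after the first and final infusions, and in the synopsis.

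The only formula is in section 9.1.1.9. It says "Data from each 72-hour period will be analyzed for mean glucose concentration" and then, as a separate output, "mean glucose variability (absolute value of measured glucose minus 5.5 mmol/L [100 mg/dl". Counts and durations of high and low episodes follow.

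Section 9.1.1 treats the measure as a construct of its own, distinct from HbA1c: "glycemic lability (MAGE and LI), hypoglycemia (Clarke and HYPO scores), glucose variability (CGMS". Section 9.1.1.3 covers lability by other means: "Glycemic lability will be assessed by both the mean amplitude of glycemic excursions (MAGE) and the lability index (LI". Both of those use capillary readings.

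The protocol gives no other formula for CGMS variability, and it does not describe this one as a distance from target or from normoglycaemia.

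**The concern.** The name and the formula describe different quantities. Variability is how far a subject's readings spread around that subject's own level. The formula averages how far the readings lie from one fixed value that is the same for everyone.

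Under section 10.2.2 a continuous secondary endpoint like this would be compared between arms by a t-test. If one arm simply has a lower mean glucose, the score can fall with no change in swings and be reported as reduced variability. Conversely, a real reduction in swings around a raised mean can leave the score unchanged. The meaning also shifts with outcome: nearer to 5.5 mmol/L the score responds to spread, and well above it the score responds to level.

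**Working it through.** **Inputs.** The reference value (5.5 mmol/L), the 72-hour trace and the separate mean glucose output come from section 9.1.1.9. The trace means, SDs and shapes below are assumptions, because the protocol gives none. The protocol states no figure for this endpoint that could be reproduced. The unit conversion is consistent: 5.5 × 18.016 = 99 mg/dL, printed as 100.

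**Step 1: algebra, no distribution assumed.** For any reading G, |G − 5.5| = (G − 5.5) + 2 × max(5.5 − G, 0). Averaging over the trace:

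score = (mean G − 5.5) + 2 × mean of max(5.5 − G, 0).

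The first term is level. Beyond that, only readings below 5.5 contribute. If there are none, score = mean G − 5.5 and spread drops out entirely.

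**Step 2: normally distributed readings.** With mean m, SD s and d = m − 5.5,

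score = s√(2/π)·exp(−d²/2s²) + d·[1 − 2Φ(−d/s)].

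| Mean | SD | Score |
|---|---|---|
| 9.0 | 0.5 | 3.50 |
| 9.0 | 1.0 | 3.50 |
| 9.0 | 3.0 | 3.86 |
| 9.0 | 4.0 | 4.34 |
| 7.0 | 1.0 | 1.56 |
| 7.0 | 3.0 | 2.69 |
| 5.5 | 3.0 | 2.39 |

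The last row has six times the SD of the first (3.0/0.5), yet it scores 32% lower (1 − 2.39/3.50). At mean 9.0, doubling the SD from 0.5 to 1.0 changes nothing. At mean 7.0, raising the SD from 1 to 3 raises the score by 72% (2.69/1.56).

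**Step 3: constructed 72-hour traces.** These use 5-minute readings, flat or sinusoidal, and do not rely on normality.

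| Trace (mmol/L) | SD | Score |
|---|---|---|
| Flat 9 | 0 | 3.50 |
| 5.5–12.5 around 9 | 2.47 | 3.50 |
| 5.5–10.5 around 8 | 1.77 | 2.50 |
| 3–11 around 7 | 2.83 | 2.73 |
| 2.5–8.5 around 5.5 | 2.12 | 1.91 |
| Flat 10 | 0 | 4.50 |
| 3–17 around 10 | 4.95 | 5.41 |

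The first two rows tie although one does not move at all. Going from flat 9 to the 5.5–10.5 trace lowers the score by 1.00 while the SD rises from 0 to 1.77. The last two rows go the other way: with the mean held at 10, a swing deep enough to cross 5.5 does score higher.

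**Step 4: which feature dominates.** Simulated sinusoids had amplitudes of 0.5 to 5, capped so that no reading fell below 2.2.

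| Range of trace means | Correlation with mean glucose | Correlation with SD |
|---|---|---|
| 7–14 | 0.99 | 0.05 |
| 6–12 | 0.97 | 0.18 |
| 5.5–8 | 0.50 | 0.83 |

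**The case against.** A reader might infer that the endpoint is simply mean glucose under another name, that any flat high trace outscores a swinging one, and that this is the usual situation in the trial. The documents do not support that reading.

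- **Level only.** The collapse to level is exact only when readings stay at or above 5.5 (or, with the sign reversed, at or below it). Traces that straddle 5.5 do register swings, as the mean 7.0 rows and the 0.83 correlation show.
- **Ranking.** The reversal holds for some pairs of traces and not others. The 3.50 against 2.39 contrast is a chosen illustration. No figure in the protocol supports an SD of 0.5 in these subjects, and a normal distribution with mean 5.5 and SD 3.0 puts a little mass below zero.
- **Frequency.** Section 9.1.1.1 asks for insulin to "maintain fasting capillary glucose levels 5-9 mmol/L". That is a fasting capillary target in insulin-treated subjects, not a 72-hour sensor distribution. Section 5.11 gives a 4 to 8 range early after transplant, and full graft function in section 4.1.3.1 calls for fasting serum glucose of 7.0 mmol/L or less. Both point to levels nearer 5.5.
- **Cover elsewhere.** LI and MAGE are efficacy endpoints at the same times and are built from glucose differences. LI is also the lability measure used for entry. The trial's lability question does not rest on CGMS.
- **Transparency.** The formula is printed beside the name, and section 10.2.2 promises qualifiers on significant secondary findings.

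The first four points stand as limits on scope. The last helps little: those qualifiers concern chance findings, not a score that measures something other than its label. Nor do LI and MAGE, taken from intermittent capillary readings, change what the CGMS endpoint reports.

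**Conclusion.** The definition is wrong for the name it carries. Mean distance from 5.5 mmol/L equals mean glucose minus 5.5 when all readings are at or above that value, and otherwise combines level and spread. A difference between arms therefore cannot be read as a difference in variability. This conclusion is algebraic and needs no assumed distribution. The sizes quoted do rest on assumed normal or sinusoidal traces.

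The documents do not show how often traces lie wholly above 5.5, so no claim is made that the endpoint usually reduces to level. The consequence is limited to one secondary endpoint. The primary endpoint, sample size and error rate are unaffected, and lability is still assessed by MAGE and LI.

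**What to change.** In section 9.1.1.9, define CGMS glucose variability as the within-subject SD of sensor glucose over the same 72-hour trace, reported with the coefficient of variation. Let the endpoint in section 4.1.3 and the synopsis refer to that definition. In the traces above, the SD reverses the misleading order: flat 10 has SD 0, and the 3–11 trace has SD 2.83 (CV 40%).

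If the distance measure is still wanted, call it mean absolute deviation from 5.5 mmol/L and report it alongside mean glucose, not as variability.

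The cost is a change of wording and one line of analysis code. The sensor data, visits and burden on subjects stay the same.

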#### 9.1.1.10 QUALITY OF LIFE (QOL)

Quality of life (QOL) will be assessed using the DTSQs and DTSQc, and the SF36 patient questionnaires.

#### 9.1.1.11 POSITRON EMISSIONS TOMOGRAPHY (PET)

In a subset of subjects (n=8, 4 LMW-DS, 4 Control) at selected sites, a minority (100 000 IEQ) of islets will be labeled with FDG and a PET/CT scan will be performed at the first transplantation. Procedures will follow established SOPs from the Nordic Network. Subjects will be informed about this sub-study after randomization and a separate informed consent will be obtained.

## 9.2 Immunologic Testing

Although insulin independence can be achieved via transplantation of an adequate number of viable, functional islets, a gradual reduction in the percent insulin independent patients occurs over time, with approximately 25% of patients still insulin free at 4 years post-transplant. Immune mediated islet destruction in the form of allorejection and/or recurrent autoimmunity, as well as attrition of a marginal islet mass due to exhaustion and/or toxicity of immunosuppressive agents, have all been postulated to play a role in islet loss. In order to begin to dissect the role of immune mediated reactions in allograft loss, tests will be done to determine if sensitization to donor allo or islet autoantigens has occurred. In addition, maintenance of protective immunity in the setting of immunosuppression will be addressed, as will the role of innate immune reactions in the early post-transplant period.

The timing of immune assays will be "reset" with additional transplants; i.e., the day of the 2nd transplant becomes day 0 and subsequent samples for immune assays are drawn in relation to this day.

#### 9.2.1 Local Center Laboratory

#### 9.2.1.1 HLA TYPING OF DONORS AND RECIPIENTS, CROSSMATCHING

HLA typing of donors and recipients, as well as crossmatching, will be done at the individual centers. HLA typing should not be repeated if previous test results are readily available. A negative crossmatch is required in order for transplantation to occur.

#### 9.2.2 Core Laboratories

#### 9.2.2.1 ALLOANTIBODY

Development of alloantibody is generally associated with longer term graft loss. Development of alloantibody specific for 1 or 2 HLA antigens can now be defined using assays that incorporate HLA specific monoclonal antibodies. The University of Pennsylvania and The Rudbeck Laboratory will provide core laboratory services for alloantibody assessments.

#### 9.2.2.2 AUTOANTIBODY

The role of autoantibody in graft loss remains unclear. The Barbara Davis laboratory in Denver, CO will provide core lab service for autoantibody assessments.

#### 9.2.2.3 ARCHIVED SERUM, CELLS, RNA, AND PLASMA

Specimens that are collected for the purpose of archiving will be registered in the biobank, re-labeled and shipped from Uppsala, Sweden to the NIDDK repository. The study Manual of Procedures details the procedures for de-identifying and batch shipping specimens to the United States.

In order to ensure that we will ultimately gain as much information as possible from these trials, and due to the ongoing development of, e.g., T cell assays, serum, cells and RNA will be archived for future analyses.

#### Serum (NIDDK Repository)

• Blood will be collected to obtain serum. Specimens will be collected, processed, and shipped frozen according to procedures outlined in the CIT-01 Laboratory Manual.

Peripheral Blood Mononuclear Cells (PBMC) and Plasma (NIDDK Repository)

• Blood will be collected to obtain recipient PBMC and Plasma. The specimen will be collected, processed and shipment frozen according to procedures outlined in the CIT-01 Laboratory Manual.

RNA (NIDDK Repository)

• Blood will be collected to obtain RNA. Specimens will be collected, processed, and shipped frozen according to procedures outlined in the CIT-01 Laboratory Manual.

RNA and Plasma (The Rudbeck Laboratory)

• Blood will be collected to obtain RNA. The specimen will be collected, processed, and shipped frozen to The Rudbeck Laboratory, according to procedures outlined in the CIT-01 Laboratory Manual.

#### 9.2.2.4 THROMBIN-ANTITHROMBIN COMPLEXES, C3A AND C-PEPTIDE

IBMIR is triggered by tissue factor expressed by the islets of Langerhans. After infusion of the islet into the portal vein the IBMIR is triggered by tissue factor (TF). IBMIR is reflected in the generation of the coagulation and complement markers, thrombin-antithrombin (TAT) and C3a, and release of Cpeptide from the islet indicates islet damage. C-peptide, TAT and C3a are assayed by ELISA. There are no international calibrators for TAT or C3a which necessitates that these samples are measured at the same site if inter-laboratory variations are to be avoided.

Thrombin-antithrombin (TAT) complexes have been instrumental in demonstrating IBMIR in subjects. Initial high levels have also been shown to correlate with low levels of fasting C-peptide 7-14 days after transplantation indicating poor function. Complement activation and generation of C3a is associated with a strong IBMIR. Release of C-peptide directly after the islet infusion reflects damage to the islets.

The Rudbeck Laboratory in Uppsala, Sweden will provide core lab service for TAT, C3a, and C-peptide assessments. In order to correlate expression of proinflammatory or procoagulant markers on islets with recipient response in the early post-transplant period, EDTA anti-coagulated blood (3 mL at each time point) will be collected immediately prior to islet infusion, when 125 mL is left in the infusion bag (before rinsing), and at 0, 15, 60, 180, 270, 360 minutes after the completion of the islet infusion, and 24 hours post-infusion for assessment of TAT, C3a and c-peptide levels. The EDTA-blood should be centrifuged and the plasma stored at -70°C. The samples shall be shipped (without previous thawing) on dry ice to The Rudbeck Laboratory in Uppsala, Sweden.

### 9.2.2.5 ADDITIONAL ANALYSES

Additional analysis will also be performed to further characterize the IBMIR, growth factors and additional inflammatory parameters. These analyses, the time points and the amount of blood required are summarized in Appendix I- Schedule of Events.

## 10. STATISTICAL CONSIDERATIONS AND ANALYTICAL PLAN

# 10.1 Analysis Samples

The primary analysis will use the intent-to-treat principle and all subjects will be analyzed in the group to which they were randomized. Safety analyses will be based on treatment received. A secondary per protocol analysis will include data for those subjects who provided data at 75 days and who had no major protocol deviations.

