# **Study Definitions Page**

Control Arm- State of the Art	The study treatment group randomized to receive protocol specified immunosuppression without LMW-DS, including anticoagulative treatment with Heparin with the islet infusion.
Experimental Arm- Low Molecular Weight Sulfated Dextran	The study treatment group randomized to receive protocol specified immunosuppression with Low Molecular Weight Sulfated Dextran (LMW-DS), and excluding Heparin treatment.
Full Islet Graft Function	
 
Islet transplant recipients are considered to have full islet graft function if all of the following criteria are met: 
 
Titrated off insulin therapy for at least 1 week (7 consecutive days) with the last day within the day 75 and day 365 windows;
 
One HbA1c level, one fasting serum glucose level, and Mixed Meal Tolerance Test are documented within the visit window (e.g. 70-80 days at Day 75) and 7 consecutive days of blood sugar and insulin readings are documented within +/- 7 days of the visit window (e.g. 63-87 days at Day 75);
 
HbA1c <7.0% or a ≥2.5% decreased from baseline;
 
Fasting capillary glucose level should not exceed 140 mg/dL (7.8 mmol/L) more than three times in the 7 consecutive days (fasting is defined as 1st blood sugar reading of the day not noted as post-prandial or bedtime). Post-prandial capillary glucose level ≤ 126 mg/dL (≤7.0 mmol/L) at 90 minutes during the MMTT;
 
Fasting serum glucose level ≤ 126 mg/dL (≤7.0 mmol/L) from central lab results; if the fasting serum glucose level is > 126 mg/dL (>7.0 mmol/L), it must be confirmed in an additional one out of two measurements;
 
At least one MMTT fasting or stimulated c-peptide ≥0.5 ng/ml.
 
 
 

Graft Failure	Islet allograft failure will be defined as absence of insulin production by transplanted islets, as evidenced by absence of c-peptide <0.1nmol/L (<0.3 ng/mL). This will be determined by: (1) c-peptide <0.1nmol/L (<0.3 ng/mL) on random testing, followed by (2) c-peptide <0.1nmol/L (<0.3 ng/mL) at baseline, and at 60 and 90 minutes after MMTT. C-peptide levels obtained in the course of the MMTT levels will be run at the core laboratory in Seattle, WA. Subjects with graft failure do not need to complete the day 75 metabolic assessment.

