Immune Sensitization Insulin Dependent	Defined by detecting anti-HLA antibodies not present prior to transplantation Islet transplant recipients who do not meet the criteria for full islet graft function will be
Intensive Diabetes Management	considered insulin-dependent. Self monitoring of glucose values no less than a mean of three times each day averaged over each week and by the administration of three or more insulin injections each day or insulin pump therapy.
Partial Graft Function	Islet transplant recipients who do not meet criteria for full islet graft function but have either a basal or stimulated C-peptide level $\geq 0.1$ nmol/L ( $\geq 0.3$ ng/L).
Primary Non- Function	Graft failure that occurs between 3-7 days post-transplant. Participants with graft failure do not need to complete the day 75 metabolic assessments.
Progressive Renal Dysfunction	A creatinine rising above 2.0 mg/dL (177 $\mu$ mol/L) with calcineurin inhibitor trough levels within maintenance levels.

Protocol Eligible	After completion of the screening assessments required to confirm eligibility, the subject is considered "protocol eligible".
Severe Hypoglycemic Event	A severe hypoglycemic event is defined as an event with one of the following symptoms: memory loss; confusion; uncontrollable behavior; irrational behavior; unusual difficulty in awakening; suspected seizure; seizure; loss of consciousness; or visual symptoms, in which the subject was unable to treat him/herself and which was associated with either a blood glucose level < 54 mg/dL (3.0 mmol/L) or prompt recovery after oral carbohydrate, IV glucose, or glucagon administration.
Wait List	Protocol eligible subjects who have been listed for islet transplant on the Nordic islet transplant wait list.

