## 5.15.3 Premature Discontinuation of Study Treatment

Study treatment may be prematurely discontinued for any subject for any of the following reasons:1.

The subject is unwilling or unable to comply with the protocol.2. The investigator believes that the study treatment is no longer in the best interest of the subject.3. Graft Failure: Islet allograft failure will be defined as absence of insulin production by transplanted islets, as evidenced by absence of c-peptide <0.1nmol/L (<0.3 ng/mL). This will be determined by (1) c-peptide <0.1nmol/L (<0.3 ng/mL) on random testing, followed by (2) c-peptide<0.1nmol/L (<0.3 ng/mL) at baseline, and at 60 and 90 minutes after MMTT. C-peptide levels obtained in the course of the MMTT levels will be run at the core laboratory in Seattle, WA. Subjects with graft failure do not need to complete the day 75 metabolic assessments.

4. A unexpected related serious adverse event. The agent(s) to which the event is attributed will be discontinued.

Subjects who prematurely discontinue study treatment will remain in the study until normal termination, for the purpose of monitoring safety and efficacy parameters and will enter the reduced

schedule outlined in Appendix 2. Data from these subjects will be used in the intent-to-treat analysis. 6. Criteria for Premature Termination of the Study

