#### **10.2.1 PRIMARY ENDPOINT**

The primary endpoint is the level of stimulated c-peptide at 90-minutes derived from the mixed-meal tolerance test (MMTT) at 75±5 days following the first islet infusion. The difference in the means between the two treatment groups will be used as the measure of efficacy. Because the sample size is small, it is not practical to adjust for treatment center. The primary analysis will be based on an independent samples two-sided t-test. A difference will be declared statistically significant if  $p \le 0.05$ . The effect size will be estimated by the observed difference in the means for the two treatments. The estimated effect size and a 95% confidence interval for the effect size will be reported. If there is compelling evidence that the normal distribution does not hold then a logarithmic or square root transformation will be done before using the t-test. Appropriate adjustments will be made to compute the estimated effect size and its confidence interval.

The primary endpoint should be available in all randomized subjects. However, should a value not be available for a subject then a value will be imputed in one of two ways. If a value is observed for a subject after the 75 day period but before any subsequent islet infusion then that value will be used in the analysis. If no later value is available (e.g. the subject dies or withdraws from the study) then the lowest value observed for all subjects will be imputed for that subject. All imputations will be reported with the primary analysis. A secondary sensitivity analysis using multiple imputation methods will be performed to examine the effect of the choice of this imputation strategy.

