## APPENDIX 2. REDUCED FOLLOW-UP SCHEDULE

Subjects withdrawn from study therapy should be followed according to the reduced follow-up schedule provided below. All reduced follow-up assessments should be scheduled relative to the day on which the study treatment is discontinued. The last follow-up visit will vary depending on when the subject discontinues study therapy and should be done at 1-year post the subject's **last** transplant.

Complete the following assessments at the intervals (+/- 7 days) indicated below relative to the day the subject discontinued study treatment. Continue conducting these assessments at the defined intervals until the subject reaches one year post **last** transplant.

- Assess SAEs and hypoglycemic events: q1 month. If subject does not come to the study site for the visit, attempt to obtain information via a phone contact.
- Alloantibody (central lab): q 1 month for the first 3 months and q 3 months thereafter.

Complete the following assessments at 1-year (+/- 14 days) post initial transplant:

- Assess SAEs and hypoglycemic events
- Alloantibody (central lab)
- HbA1c (central lab)
- 90 minute c-peptide post MMTT (central lab)
- Serum creatinine (central lab)
- QOL questionnaire (via mail or in-person)

Complete the following assessments at 1-year (+/- 7 days) post **last** transplant:

- Assess SAEs and hypoglycemic events
- QOL questionnaire (via mail or in-person)

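### The secondary per-protocol set requires Day-75 data, yet graft failures are excused from the Day-75 assessment, so compliant subjects can drop out because of the efficacy outcome

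*Protocol*

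**What the plan says.** Section 10.1 of the protocol sets two conditions for the supportive set: "A secondary per protocol analysis will include data for those subjects who provided data at 75 days and who had no major protocol deviations". Having Day-75 data and being free of major deviations are separate requirements, and both must be met.

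The Study Definitions Page says under Graft Failure: "Subjects with graft failure do not need to complete the day 75 metabolic assessment". Under Primary Non-Function, defined as graft failure 3 to 7 days after transplant, it says: "Participants with graft failure do not need to complete the day 75 metabolic assessments". Sections 5.15.3 and 6.2 repeat the exemption. The Day-75 visit includes the mixed-meal tolerance test (MMTT) that yields the primary endpoint (section 4.1.1 and Appendix 1).

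For the primary analysis, section 10.1 says: "The primary analysis will use the intent-to-treat principle and all subjects will be analyzed in the group to which they were randomized". Section 10.2.1 handles a missing value by taking a later one obtained before any further infusion; failing that, "then the lowest value observed for all subjects will be imputed for that subject". That rule is written for the primary analysis. Nothing in the protocol keeps exempted subjects in the per-protocol set or assigns them a value there.

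**The concern.** A per-protocol set is meant to exclude people who did not follow the protocol. Here a subject can follow it in every respect, lose the graft early, use an exemption that the protocol grants, and be excluded for lack of Day-75 data. The reason for exclusion is then a post-randomization event that is itself the worst value of the efficacy outcome.

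The primary objective (section 2.1) is to see whether LMW-DS enhances engraftment and prevents the early inflammatory reaction that destroys islets. Early failure is thus one of the ways in which the arms might differ. If it is more common in one arm, removing failures makes that arm look better in the per-protocol comparison. The per-protocol and primary results could then disagree because of how the set was built, and a reader might take the disagreement for information about adherence.

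**Working it through.** **1. The plan's own figure.** The protocol gives no number for the per-protocol set. Its design figures (section 10.4) are 18 per arm, SD 0.9 nmol/L, and a two-sided 5% t-test.
- Standard error = 0.9 × √(2/18) = 0.30 nmol/L, with 34 degrees of freedom.
- Difference 1.0: noncentrality 1.0/0.30 = 3.33, power 89.9% against the stated 90%. This reproduces.
- Difference 0.9: noncentrality 3.0, power 83.0% against the stated 80%. The statement is conservative and has no bearing here.

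**2. Following one subject through the text.** Take a compliant subject with primary non-function.
- The Day-75 assessment is not required (Study Definitions Page, 5.15.3, 6.2).
- Graft failure is a listed reason for stopping study treatment, and those who stop enter reduced follow-up (5.15.3). The only MMTT C-peptide listed there is at 1 year after the initial transplant (Appendix 2).
- With approval, a failed graft may be re-transplanted before Day 75 (7.4.2). The follow-up clock then restarts (7.5, 7.7), so a Day-75 value after the first infusion may never exist.
- Under 10.1 the subject is analysed as randomized in the primary analysis, with a value under 10.2.1, but does not qualify for the per-protocol set.

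**3. Expected differences.** The failure rates and means are assumptions. Let f_C and f_T be the failure rates on control and LMW-DS, μ the mean of functioning grafts (equal in both arms for now), and 0.05 nmol/L the mean of failed grafts, which lies below the protocol's failure threshold of 0.1 nmol/L.
- All subjects: difference = (f_C − f_T) × (μ − 0.05).
- Failures dropped: difference = μ − μ = 0.

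| Failure, control v LMW-DS | μ (nmol/L) | All subjects (nmol/L) | Failures dropped |
|---|---|---|---|
| 20% v 5% | 1.5 | 0.15 × 1.45 = 0.22 | 0 |
| 10% v 10% | 1.0 to 2.0 | 0 | 0 |
| 30% v 0% | 2.0 | 0.30 × 1.95 = 0.585 | 0 |

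Over control rates of 10–30%, LMW-DS rates of 0–10% and means of 1.0–2.0 nmol/L, the all-subject difference runs from 0 to 0.585 nmol/L.

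**4. Simulation with the protocol's lowest-value rule.** Settings: 18 per arm, functioning grafts drawn from mean 1.5 and SD 0.9 in both arms (values below 0.1 set to 0.1), failures given the lowest observed value, 4,000 runs per row.

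| Failure, control v LMW-DS | Mean difference, kept | Mean difference, dropped | Rejection rate, kept | Rejection rate, dropped | Expected per-protocol n, control / LMW-DS |
|---|---|---|---|---|---|
| 20% v 5% | 0.218 | 0.005 | 10.5% | 4.7% | 14.4 / 17.1 |
| 30% v 10% | 0.273 | −0.005 | 13.9% | 4.8% | 12.6 / 16.2 |
| 40% v 10% | 0.418 | 0.004 | 27.1% | 5.3% | 10.8 / 16.2 |
| 10% v 10% | −0.001 | 0.001 | 5.0% | 5.4% | 16.2 / 16.2 |

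**5. Relaxing the equal-means assumption.** With functioning means μ_C and μ_T, the all-subject difference exceeds the failures-dropped difference by f_C(μ_C − 0.05) − f_T(μ_T − 0.05). Assume, for example, μ_C = 1.5, μ_T = 2.0 and failure of 20% v 5%. The gap is 0.20 × 1.45 − 0.05 × 1.95 = 0.29 − 0.0975 = 0.19. The failures-dropped difference is 0.50 and the all-subject difference 0.69 nmol/L. The per-protocol difference is then attenuated, not zero.

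**The case against.** Several points on the other side are sound.

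- **Only a supportive analysis is touched.** The primary analysis includes every randomized subject and has an imputation rule, with multiple imputation as a sensitivity analysis (10.2.1). The stopping boundaries in 10.6 do not refer to the per-protocol set. This stands.
- **The exemption is permissive.** A reader might infer that the per-protocol set compares surviving grafts only. The text does not say so: it releases failed grafts from the assessment but does not bar them from it. The third stopping rule in 6.2 counts subjects with C-peptide below 0.3 ng/mL at 75 days, so some failed grafts are expected to have Day-75 data. This stands.
- **Harm would not be concealed.** A reader might also infer that excess failures on LMW-DS could go unseen. Primary non-function can suspend the study or a site (6.2, 6.3), full graft function is an endpoint at Days 75 and 365, and unevaluated dichotomous endpoints are in general imputed as failures (10.2.2). What can mislead is the per-protocol contrast, not the trial's whole picture.
- **The zero is built in.** It follows from assuming equal functioning means. Section 5.2.2 describes a graded benefit, more islets surviving, under which functioning grafts would differ too. This stands; step 5 shows that distortion remains, but not complete loss of the effect.
- **Details belong to the SAP, and the rule is loosely worded.** Section 10.1 does not say which Day-75 data are needed, although the primary endpoint is the natural reading, and 10.2 defers detail to the SAP. This carries less weight. The protocol itself fixes the membership rule, and 10.7 requires an amendment to change principal features of the analysis plan.

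**Conclusion.** The point holds for the secondary per-protocol analysis. Its membership rule and the graft-failure exemption together allow compliant subjects to be excluded because their grafts failed, and the comparison is biased if failure rates differ by arm. The actual size is unknown because the protocol gives no failure rates by arm.

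The loss from 0.22 to 0 nmol/L is an illustration that rests on 20% v 5% failure, equal functioning means of 1.5 nmol/L, failed grafts at 0.05, and every early failure going untested at Day 75. If some failures are tested then, the distortion is smaller. With equal failure rates and equal functioning means there is none. The documents do not support extending the criticism to the primary result or to safety monitoring.

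**What to change.** In section 10.1, and in the SAP to match:

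- Define the per-protocol set as randomized subjects with no major protocol deviation who have either a Day-75 90-minute C-peptide or graft failure confirmed by the protocol's own definition before Day 75.
- State that absence of the Day-75 test under the graft-failure exemption is not a reason for exclusion.
- Give these subjects the value that they carry in the intent-to-treat analysis under 10.2.1, so that one failed graft does not have two values. As a sensitivity analysis, use the 90-minute C-peptide from the confirmatory MMTT.

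The cost is a sentence or two. No new data are needed, because declaring graft failure already calls for C-peptide at baseline, 60 and 90 minutes of an MMTT, run at the core laboratory. The small downside is that some per-protocol values would be imputed and not measured at Day 75. The confirmatory value may come from the first week after transplant, which is why it suits a sensitivity analysis better than the main one.
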